2 DEFINITIONS

Baseline: The assessments performed prior to the study injection after the Screening Visit.

Blinded Evaluator: The Blinded Evaluator will be a physician, research nurse, registered physiotherapist or physician assistant trained by the PI to perform the assessments outlined in the protocol. The Blinded Evaluator will complete the physical evaluation of both knees, range of motion (ROM) assessment of both knees, and the Evaluator Global Assessment.

End of Study: End of study is defined as the last subject's last visit.

Enrolled: A subject who has signed the informed consent form (ICF) is enrolled.

Index Knee: The knee that meets the eligibility criteria for treatment. The index knee may also be termed the "study knee". In subjects with bilateral knee Osteoarthritis (OA), where both knees meet eligibility criteria, the more symptomatic knee is the index knee.

Ethics Committee (EC): EC refers to an independent body (e.g. Research Ethics Boards, Independent Ethics Committees) whose responsibility is to ensure the protection of rights, safety and well-being of human subjects involved in a trial. Committees with these responsibilities will be referred to in this document as Ethics Committees.

Rescue Medication: Acetaminophen/paracetamol will be distributed as the rescue medication. It is the only medication that should be taken for knee pain during the entire study. Rescue medication will be discontinued at least 48 hours prior to Baseline and all follow-up visits.

Treating Physician: The Treating Physician will most often be the Principal Investigator (PI). He/she will administer the Cingal®, Monovisc® or steroid injection but will not participate in the efficacy evaluation.

Treatment Failure: A subject who undergoes a procedure or uses a medication (other than the rescue medication) for the treatment of OA in the index knee at any time after the study injection through the 39 week visit.

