Subjects meeting the inclusion/exclusion criteria for Cingal 16-02 will have been randomized to receive a single injection of Cingal, Monovisc or triamcinolone hexacetonide (TH) in the index knee. Since there is a difference in volume between Cingal, Monovisc and TH, the treating physician is not considered blinded. To maintain the double-blind design of the study, there is a person assigned to the role of Treating Physician and one person assigned to the role of Blinded Evaluator. The Treating Physician, most often the PI, will administer the injection but will not participate in the evaluation of study treatment effectiveness. A second individual, designated as the Blinded Evaluator, is blinded to treatment and will complete the pre- and post-treatment Evaluator Global Assessment, knee exams and ROM measurements. To maintain the subject blinding, the injection syringe will have been prepared separate from the patient and the injection will be masked from the subject. The blinding of the patient and the blinded evaluator will be maintained in both the Cingal 16-02 and Cingal 17-02 trials.

The subject will have been trained on how to complete the WOMAC, Patient Global Assessment and

EuroQol within the Cingal 16-02 trial. The subject should complete these questionnaires prior to any physical evaluation that must be done at the 39 week follow-up visit.

The Blinded Evaluator will collect and record AEs from the subjects and consult the Treating Physician only as needed in the management of AEs. The Blinded Evaluator will be a physician, research nurse, registered physiotherapist or physician assistant trained to perform the assessments outlined in the protocol (Section, 10.1 Schedule of Events).

Up to 40 sites in Europe are participating in the study to enroll 576 subjects. Subject participation in this extension study will last approximately 13 additional weeks beyond the Cingal 16-02 trial with follow-up the visit scheduled at weeks 39 after the treatment injection in Cingal 16-02.

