10.2.17 Blinding

During the Cingal 16-02 trial the Treating Physician will have been aware of the differences between the Clinical Trial Materials and will have been unblinded, therefore; there were two clearly defined roles of a **Treating Physician** (unblinded) and a **Blinded Evaluator** (blinded) at each site. The site personnel fulfilling these roles will remain the same in Cingal 16-02 and Cingal 17-02.

- **Treating Physician:** The Treating Physician is most often the PI. He/she will have administered

the Cingal, Monovisc or Triamcinolone Hexacetonide (TH) injection but will not participated in the efficacy evaluations in either Cingal 16-02 or Cingal 17-02.

- **Blinded Evaluator:** The Blinded Evaluator will be a physician, research nurse, registered physiotherapist or physician assistant trained by the PI to perform the assessments outlined in the Cingal 16-02 and Cingal 17-02 protocols. The Blinded Evaluator will have completed the physical evaluation of both knees, ROM assessments of both knees, and the Evaluator Global Assessment for both Cingal 16-02 and Cingal 17-02 trials.

The identity of the syringes would not have been revealed during the Cingal 16-02 trial to the patients or the blinded evaluator. This blinding of the treatments given to the patients in the Cingal 16-02 trial will be maintained for the patients and the blinded evaluators in the Cingal 17-02 trial.

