10.4 Post-Treatment Follow-Up

All study subjects will have follow-up assessments at 39 weeks after injection day in Cingal 16-02 to evaluate effectiveness of the treatment and to assess AEs and protocol compliance. The Blinded Evaluator will evaluate the clinical status of the subject at each visit.

More than 48 hours prior to the visit, the subject will be reminded of the visit date and time, the need to abstain from acetaminophen/paracetamol for at least 48 hours prior to each follow-up visit and the requirement to bring their subject diary and the acetaminophen/paracetamol for a pill count with them to the appointment.

If the subject arrives for a study visit without discontinuing acetaminophen/paracetamol for at least 48 hours prior to the visit, the visit should be rescheduled within the allowed window of time. Study assessments should be performed as soon as possible and the protocol deviation, if applicable, recorded in the source and eCRF. The subject must be re-educated about the importance of protocol compliance.

If the subject does not come in at the expected time, at least three attempts will be made to contact the subject in order to accomplish maximum subject compliance with the follow-up schedule.

The following post-treatment visits will be performed. The subject will be asked whether any concomitant medications have been taken. All assessments will be done by the Blinded Evaluator.

39 Weeks \pm 7 Days

- Confirm Rescue Medication Washout
- Evaluate Subject Diary
- Count Rescue Medication Pills (if needed)
- Physical Evaluation (both knees)
- ROM (both knees)
- WOMAC (both knees)
- Patient Global Assessment
- Evaluator Global Assessment
- EuroQol
- Assess Concomitant Medications

- Assess AEs

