11.3 Relationship

The Relationship between an AE and the CTM will be determined by the Investigator on the basis of his or her clinical judgment and the following definitions:

Definitely Related: The AE follows a reasonable temporal sequence from administration of the CTM; the AE follows a known or expected response pattern to the CTM.

Probably Related: The AE follows a reasonable temporal sequence from administration of the CTM; the AE follows a known or expected response pattern to the CTM; and the AE could not be reasonably explained by the known characteristics of the subject's clinical state.

Possibly Related: The AE follows a reasonable temporal sequence from administration of the CTM; the AE follows a known or expected response pattern to the CTM, but could readily have been produced by a number of other factors.

Unlikely Related: The AE which etiology is unlikely related to the CTM even if event may follow a known or expected response pattern to the CTM, and likely to be produced by a number of other factors. Sufficient information is not available at the time of the AE to determine its causality.

Not Related: An AE for which sufficient information exists to indicate that the etiology is unrelated to the CTM. One or more of the following variables apply:

- The AE does not follow a reasonable temporal sequence following administration of the CTM;
- The AE is readily explained by the subject's clinical state or other therapies.

For events that are determined to be definitely, probably or possibly related, additional information on the relationship and timing of the event in relation to the arthrocentesis and study injection will be captured.

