11.5 Reporting

11.5.1 Adverse Events

All AEs that occur after signing the ICF will be recorded. At each visit during the trial, AEs that have occurred since the previous visit must be recorded. All subjects will be questioned and evaluated for

AEs or complications associated with the procedure. Complications of the injection include, but are not necessarily limited to: pain, swelling and/or inflammation at the injection site. The Investigator will determine the severity and relationship of each event, as defined above.

AEs observed during the course of this study, regardless of severity or relationship to the injection will be recorded on the appropriate eCRF. Each reported complication/AE will also include the duration, action taken to address the AE, and the resolution status (e.g. ongoing, resolved). These subjects will continue to be evaluated for safety and efficacy at all scheduled follow-up points.

The sponsor must report the results of an evaluation of an unanticipated adverse device effect (UADE) to relevant regulatory agencies and all reviewing ECs and investigators within timelines required by the regulatory agencies.

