16.5 Pre-Study Documentation

The Investigators in Cingal 17-02 will have enrolled subjects into that study having provided the following documents prior to the enrollment of any subjects as appropriate to local country regulation:

- Completed and signed Investigator Agreement/Form FDA 1572 signed by Principal Investigator.
- Signed and dated protocol signature page by the Principal Investigator (Investigator) and all Sub-Investigators (including Blinded Evaluator).
- Signed and dated protocol amendment(s) signature page by the Investigator and all Sub-Investigators (including Blinded Evaluator), when applicable.
- Current curriculum vitae (CV) for the Investigator and all Sub-Investigators (including Blinded Evaluator)
- Current medical license for the Principal Investigator and all Sub-Investigators (if applicable).
- Financial disclosure statements signed and dated by the Investigator and all Sub-Investigator (including Blinded Evaluator).
- Copy of the EC approval letter for the protocol and any other pertinent documents.
- List of EC committee members.
- Copy of the EC-approved ICF to be used.
- Fully executed Clinical Trial Agreement.
- Delegation of Authority form.
- Certified translations of EC approval letters, and approved ICF document (when applicable).
- Insurance certificate as required.

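### Where the Principal Investigator gave the injection, the Investigator's rating of adverse-event severity and relatedness can be unblinded, and the by-arm TEAE tables depend on that rating

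*Protocol*

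**What the plan says.** On who rates, Protocol 11.5.1 states: "The Investigator will determine the severity and relationship of each event, as defined above". Protocol 11.3 states: "The Relationship between an AE and the CTM will be determined by the Investigator on the basis of his or her clinical judgment".

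On who the Investigator is, the definitions in Protocol 2 have no entry. The document checklist in 16.5 asks for "Signed and dated protocol signature page by the Principal Investigator (Investigator) and all Sub-Investigators (including Blinded Evaluator"), which equates Investigator with Principal Investigator and places the Blinded Evaluator among the Sub-Investigators. Section 16.10 makes the Investigator responsible for seeing that Sub-Investigators bring adverse events to the Investigator's attention.

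On blinding, Protocol 8.2 says: "Since there is a difference in volume between Cingal, Monovisc and TH, the treating physician is not considered blinded". Section 10.2.17 adds: "The Treating Physician is most often the PI". The same section keeps the same people in these roles for 17-02, and promises continued blinding only for the patient and the Blinded Evaluator.

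On the handling of AEs, 8.2 has the Blinded Evaluator collect and record them, consulting the Treating Physician only as needed to manage them. Section 10.4, whose 39-week list includes assessing AEs, says: "All assessments will be done by the Blinded Evaluator".

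On use of the rating, Protocol 12.4 and SAP 4.4 define TEAEs as AEs that the Investigator rated definitely, probably or possibly related. They summarise these by arm by system organ class, preferred term, severity and relationship.

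**The concern.** The trial is described as double-blind. It achieves this by separating an unblinded injector from a blinded assessor. For efficacy the separation is explicit. For AE severity and causality, the two sections that assign the rating give it to a role that the rest of the protocol most often fills with the unblinded injector.

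The relatedness scale in 11.3 turns partly on whether an event fits a known or expected response to the study material. Section 14.2.2 lists different expected reactions for hyaluronic acid and for corticosteroid. A rater who knows the arm can apply the list for that arm, and a blinded rater cannot.

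The stakes are the parts of the safety evaluation that use the rating. Severity and relationship are two of the four elements of the safety endpoint in 7.4. The TEAE definition uses relatedness rather than onset, so the rating decides which events enter the system organ class and preferred term tables at all. The suspension trigger in 11.5.5 also includes a relatedness condition.

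**Working it through.** The plan states no figure on this point, so there is none to reproduce. The check is a comparison of sections.

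1. **Rater.** 11.3 (relationship) and 11.5.1 (severity and relationship) both name the Investigator.
2. **Identity of the rater.** 16.5 equates Investigator with Principal Investigator. 16.10 has events pass from Sub-Investigators, who under 16.5 include the Blinded Evaluator, to the Investigator. Together these indicate the Principal Investigator.
3. **Knowledge of the arm.** Sections 2, 8.2 and 10.2.17 say that the Treating Physician is most often the Principal Investigator, and 8.2 says that "the treating physician is not considered blinded". Where the two roles are one person, the rater knows the arm. Where they are not, the texts do not show that the rater knows it.
4. **Safeguard.** No section requires a blinded or independent rating of severity or causality. Sections 8.2 and 10.4 give the Blinded Evaluator the collection, recording and assessment of AEs, but neither names the severity or causality rating.
5. **What depends on the rating.**
   - Dependent: the TEAE tables, the tables by severity and by relationship, SAEs by relationship (12.4; SAP 4.4), and the relatedness condition in 11.5.5.
   - Not dependent: the number of subjects with at least one AE of any causality and the Fisher test stated directly after it (12.4; SAP 4.4), AE collection by the Blinded Evaluator (8.2), and 24-hour SAE reporting, which 11.5.2 requires whatever the relationship.
6. **Scale.** Planned arm sizes from 12.1 are Cingal 256 and TH 64. Moving one subject across the boundary between possibly and unlikely related changes the arm's related-AE rate by 1/n:
   - TH: 1/64 = 0.0156, or 1.6 percentage points.
   - Cingal: 1/256 = 0.0039, or 0.4 percentage points.

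Step 6 shows only how coarse the TH rate is. It does not estimate bias. The documents give no expected AE rate, no share of events rated related, and nothing on whether ratings would differ by arm.

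7. **Reach of a change.** 17-02 adds 13 weeks after week 26 and gives no injection (section 3). Section 10.2.1 carries all 16-02 data into 17-02. Events already rated in 16-02 keep those ratings whatever is written into 17-02.

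**The case against.** The strongest reply is that the rater may in fact be blinded. Investigator is not a defined term. The equation with the Principal Investigator comes from a checklist item, and usage varies: 16.6 speaks of one or more qualified Investigators per site, and 16.7 lists Principal Investigators and Investigators separately. Section 10.4 gives the 39-week assessments, AEs included, to the Blinded Evaluator, and 8.2 limits contact with the Treating Physician to managing AEs. Effusion, an obvious local sign, is graded by the Blinded Evaluator under 10.2.9.

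Part of this stands. The identity of the rater is indicated rather than settled, and 10.4 leaves the 39-week rater ambiguous. A reader might go further and infer that 10.4 flatly contradicts 11.5.1. That does not follow. If assessing AEs means eliciting and recording them, the two sections are compatible. If it includes rating, the 39-week rater is blinded. Either way, sites cannot tell from the text who rates, and no section rules out the unblinded person.

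The second reply is that the consequences are limited. TEAEs are summarised, and no test of TEAEs is clearly specified. SAEs go to the sponsor within 24 hours regardless of relationship. Under 11.5.3, seriousness called by either the investigator or the sponsor prompts evaluation for expedited reporting. Under 11.5.5, the medical monitor in consultation with the IDMC decides whether to resume, modify or stop. All of this stands as a limit on the point. It does not protect the by-arm tables that use the rating.

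**Conclusion.** The point holds in limited form. At sites where the Principal Investigator injected, the by-arm TEAE, severity and relationship tables and the relatedness part of the suspension trigger can rest on unblinded judgement. The documents provide no blinded rating to set beside it. This assumes that Investigator means Principal Investigator, as 16.5 and 16.10 indicate.

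Three stronger readings are not supported:

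- **That every AE at every site is rated unblinded.** The overlap of roles is most often, not always, and 10.4 leaves the 39-week rater open.
- **That the whole AE comparison is unblinded.** Collection is by the Blinded Evaluator, and the stated Fisher test follows a count that ignores causality.
- **That the bias can be sized from the earlier Monovisc study in 14.2.2 (7.1% and 5.4%).** The first figure is worded as a share of AEs and the second as a share of patients. The comparison was with saline, and neither Cingal nor TH was in it.

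Size and direction of any bias are unknown. The only scale available is one subject: 1.6 points in TH and 0.4 points in Cingal on the planned arm sizes. This is a clarification worth making because it is cheap, not a defect that undermines the safety evaluation.

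**What to change.** - **Protocol 11.3, 11.5.1 and 10.4:** state that, for AEs recorded in 17-02, the Blinded Evaluator enters severity and relationship in the eCRF before any discussion with the Treating Physician. Keep the Investigator's medical rating in a separate field for safety reporting. Reconcile 8.2 and 12.4 with this wording.
- **Protocol 12.4 and SAP 4.4:** use the blinded rating for the by-arm severity and relationship tables of 17-02 events, with the Investigator-rated version beside it. Label events carried over from 16-02 as Investigator-rated.
- **Protocol 12.4 and SAP 4.4:** add a by-arm table, by system organ class and preferred term, of all AEs with onset after injection regardless of causality, so that one main safety table does not depend on the rating.

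The 24-hour SAE rule needs no change, and no additional blinded physician is needed.

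The cost is protocol and SAP wording, an extra set of rating fields in a database already being extended for 17-02 (13.1), brief site training and one more table. There are two downsides. The Blinded Evaluator may be a nurse or physiotherapist with less medical basis for judging causality, which the retained Investigator field covers. Ratings before and after week 26 will also come from different raters, which the labelling makes visible but does not remove.

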11.5.2 Serious Adverse Events/Serious Adverse Device Effects/Serious Adverse Reactions

All SAE/SADE/SAR/ SUSAR must be reported to the Sponsor or designee within 24 hours of the investigative site becoming aware of its occurrence. This requirement is irrespective of whether the SADE/SAE is thought to be possibly related to the CTM or not.

SAE/SADE/SAR/ SUSAR Reporting Procedures

Information such as the investigator name, study name/protocol number, subject ID number, the name of the SAE/SADE/SAR, the investigator's assessment as to the relationship to the CTM, and the reporting source should be included in the initial report. Any additional supporting documentation (e.g., autopsy report, hospital records, etc.) must be submitted to the Sponsor or designee. This also includes forwarding pertinent follow-up information (e.g., hospital discharge summary) as it becomes available. A completed SAE/SADE/SAR/ SUSAR form needs to be submitted with each follow-up. The subject must be monitored carefully until the condition disappears or the etiology is identified.

All SAE/SADE/SAR/ SUSAR will be entered into the EDC system. The EDC system will automatically notify the medical monitor and the Sponsor or designee.

11.5.3 Expedited Reporting

Any unexpected fatal or life-threatening AEs will be reported by the Sponsor or designee to the appropriate regulatory authorities in accordance with applicable expedited reporting guidelines. Any event considered serious by either the investigator or sponsor will be evaluated by the sponsor for expedited reporting.

11.5.4 Independent Data Monitoring Committee

An Independent Data Monitoring Committee (IDMC) will review the data to assess if the trial should be revised or closed. This IDMC will be made up of individuals who have expertise in the field, experience in the conduct of clinical trials, and/or statistical knowledge without conflicts of interest which may affect objectivity. The IDMC will operate in accordance to the IDMC Charter. A Sponsor signed and dated original of this document will be kept in the Sponsor's study files.

11.5.5 Study Discontinuation

Enrollment will be suspended if a subject experiences a serious and/or life-threatening AE that is probably or definitely related to the study injection. The study will be stopped if in the opinion of the PI, medical monitor, and Sponsor that the safety of subjects is uncertain. The decision to resume enrollment, permanently discontinue the trial, or otherwise modify the study will be made by the Medical Monitor in consultation with the IDMC. Additionally, the triggering of the stopping rules will prompt notification to the appropriate regulatory agencies including the Competent Authorities and the ECs.

12 STATISTICAL CONSIDERATIONS

The statistical analysis of the study is described in detail in a separate version-controlled prospective Statistical Analysis Plan (SAP). However, the statistical methodology described in this section of the protocol will be the basis for the detailed SAP.

12.1 Sample Size

The sample size for Cingal 16-02 was based on the primary comparison in the study between Cingal and triamcinolone hexacetonide with respect to the difference in the change in the WOMAC pain score from baseline at 26 weeks after study injection. The first secondary comparison is between Cingal and Monovisc with respect to the difference in the change in the WOMAC pain score from baseline at 3 weeks after study injection. All comparisons are made using a 5% significance level. The primary comparison is powered at 90% power and in a 2:1 randomization requires 128 patients in the Cingal group and 64 in the triamcinolone hexacetonide group. It is assumed that the difference in the mean responses for Cingal and triamcinolone hexacetonide at 26 weeks would be 10 mm based on previous clinical trials of similar viscosupplementation products [20, 21] and the Cingal 13-01 trial with a standard deviation of 20. The sample size calculation is based upon a t-test. The sample size that is necessary to detect that specified difference at a power of 90% with a significance level of 5% in a 2:1 enrollment ratio is 128 in the Cingal group and 64 in the triamcinolone hexacetonide group.

It is further assumed that the difference between Cingal and Monovisc at 3 weeks will be 5 mm and a standard deviation of 20 mm, thus it will require a minimum of 253 patients in each group to detect that difference at 80% power. With the triamcinolone hexacetonide group set at 64 patients, the number of patients in the Cingal and Monovisc groups will be increased to provide a 4: 1 randomization ratio. This will yield 256 in the Cingal group, 256 in the Monovisc group and 64 in the triamcinolone hexacetonide group. This provides a total sample size of 576 patients.

Since the primary analysis in this study is an intent to treat analysis and the missing data for a patient will be imputed using mixed effects models, no drop out rate will be assumed for this study. Thus the total sample size for Cingal 16-02 was set at 576 patients.

